7.4 Special Statistical/Analytical Issues

7.4.1 Discontinuations and Missing Data

7.4.1.1 Subject discontinuation and missing effectiveness data

To account for missing effectiveness data for the primary endpoint, missing MIHAS data will be imputed as no change (i.e. subject is considered as non-responder). This approach is conservative because it assumes that missing values are attributable to lack of treatment benefit. Furthermore, given that the primary effectiveness is only performed at baseline and Month 2 post last injection (i.e., either baseline treatment or touch-up, if applicable), the only observation that can be imputed for a missing Month 2 after the last injection time point is the baseline value, which assumes no change. Additionally, analyses will also be performed using the OC method where no missing value imputations will be conducted.

[figure not shown]

[figure not shown]
7.4.1.2 Imputation of safety data

Adverse events

For the imputed analysis start date of AEs (variable ASTDT in the ADaM domain ADAE) the following imputation rules related to any treatment period were used if applicable (only relevant for treated subjects):

Figure 1: Possible start/end dates of AEs

(Non) TEAE = (Non) Treatment Emergent Adverse Event

- 1a) If the start date is missing completely and the end date and time* does imply end before first injection then no imputation of start date and time will be performed.
- 1b) If the start date is partially missing and the partially missing start date and/or the end date and time* imply start and/or end before first injection then the missing start day/month is set to 1, if applicable, and start time (if not available) is set to 23:59, if not after end date/time (else start time is set to end time) (e.g., start date of AE is 2008-11, end date of AE is 2009-02-01, end time is 22:00, and first injection is 2008-12-06 T17:35 → imputed start date and time are 2008-11-01 23:59). Set imputation flags accordingly.
- 2a) If the start date is missing completely and end date and time* do not imply end before first injection then imputed start date is set to date of first injection and set start time (if not available) to 23:59, if not after end date/time (else start time is set to end time) (e.g., start date of AE is missing, end date of AE is 2008-12-31, end time is 23:00, and first injection date is 2008-12-06T17:35 → imputed start date and time are 2008-12-06 23:59). Set imputation flags accordingly.
- 2b) If the start date is partially missing and the non-missing part is the same as in first injection date and the end date and time* do not imply end before first injection, then the imputed start date is set to the first injection date and start time (if not available) to 23:59, if not after end date/time (else start time is set to end time) (e.g., start date of AE is 2008-

[figure not shown]
12, end date of AE is 2008-12-31, end time is 23:00, and first injection date is 2008-12-06T17:35 → imputed start date and time are 2008-12-06 23:59). Set imputation flags accordingly.

3) If the start date is partially missing and imputation rule 1b and 2b do not fit, then missing day/month is set to 1, if applicable and start time (if not available) is set to 23:59, if not after end date/time (else start time is set to end time) (e.g., start date of AE is 2009-02, end date of AE is 2009-02-01, end time is 22:00, and first injection is 2008-12-06T17:35 → imputed start date and time are 2009-02-01 22:00). Set imputation flags accordingly.

End date or end time will not be imputed.

* The end date and time may be complete, partially missing, or completely missing.

For any missing data of adverse events, a worst case strategy will be applied for all analysis tables. The intensity will be imputed by the worst intensity “severe”, the causal relationship will be imputed by the worst relationship “drug related”. Missing data of the worst outcome will be imputed by “unknown”.

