5 ANALYSIS SETS

The following analysis sets are defined for the statistical analysis of this clinical study:

Safety Population (SP)

The SP consists of all randomized subjects who received at least one study treatment in the active treatment group or who were randomized into the control arm.

Intent-to-Treat Population (ITT)

The ITT consists of all randomized subjects. This will be the primary population used for the effectiveness analyses. All effectiveness endpoints will be analyzed as randomized.

Per Protocol Population (PP)

The PP is a subset of subjects in the ITT population without major protocol deviations. Final determination of what constitutes major or minor protocol deviations will be made prior to database lock.

Subjects which have not been treated according to the randomization list will be excluded from PP. In general, tables performed on the SP will present subjects as treated and tables performed on the ITT will present subjects as randomized. In the subject data listings, the randomized treatment arm will be listed except for the section 16.2.7 (Adverse events) and 16.2.8 (Other safety variables): here the actual treatment arm will be listed.

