7.2 Safety Endpoints

All safety analyses will be performed on the SP. Summary tables will be stratified by actual treatment received and not by randomized treatment arm.

Adverse events

All AEs will be coded according to the Medical Dictionary for Regulatory Activities (MedDRA) version in effect at the time the database is closed.

TEAEs are defined in the following way:

- Treated subjects: all AEs with onset or worsening at or after the first administration of study treatment
- Not treated subjects: all documented AEs.

For treated subjects, TEAEs will be allocated to two different periods:

- Period 1: AEs with onset or worsening on or after date and time of the first administration of study treatment and up to Month 2 visit.
- Period 2: AEs with onset or worsening after Month 2 visit.

All analysis will be performed by period and overall, whereby only analysis for period 1 will be stratified by actual treatment arm. For the interim analysis, only time period 1 will be analyzed. Based on the exact number of TEAEs that will be documented in period 2, some of the summary tables may be omitted. A separate listing that contains only TEAEs of period 2 will be added.

An overall summary of AEs will be provided for the following, any line that is not applicable may be deleted in the final table:

- Any AEs

- Any non-TEAEs (for treated subjects)
- Any TEAEs
- Any treatment-related TEAEs (for treated subjects)
- Any serious TEAEs
- Any serious treatment-related TEAE (for treated subjects)
- Any TEAEs leading to discontinuation
- Any treatment-related TEAEs leading to discontinuation (for treated subjects)
- Any fatal TEAEs
- Any treatment-related fatal TEAEs (for treated subjects)

Incidences will be provided for the following classes of AEs:

- TEAEs, subjects with TEAEs and number of TEAEs by system organ class (SOC) and preferred term (PT)
- TEAEs, subjects with TEAEs by PT
- TEAEs by worst intensity, subjects with TEAEs by PT
- Related TEAEs by worst intensity, subjects with TEAEs by PT
- TEAEs by worst causal relationship, subjects with TEAEs by PT
- TEAEs by worst outcome, subjects with TEAEs by PT
- TEAEs by maximum duration, subjects with TEAEs by PT (1-3 days, 4-7 days, 8-14 days, ≥ 15 days)
- Treatment related TEAEs, subjects with TEAEs and number of TEAEs by SOC and PT
- TESAEs, listing of subjects (in case of more than 15 TESAEs respective table by SOC and PT will be provided)
- Deaths, listing of all serious TEAEs leading to death

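### Missing AE causality is imputed as related without limiting the rule to injected subjects, so an untreated control's event could be tabulated as related

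*SAP*

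**What the plan says.** SAP 7.4.1.2 (Imputation of safety data) ends with a general rule: "For any missing data of adverse events, a worst case strategy will be applied for all analysis tables". Under it, missing intensity becomes severe, and "the causal relationship will be imputed by the worst relationship", which the SAP names as *drug related*. The start-date rules earlier in that section are marked "only relevant for treated subjects". The causality rule has no such mark.

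Controls reach the AE tables by three steps:
- SAP section 5 defines the safety population as randomized subjects who were treated in the active group "or who were randomized into the control arm". Protocol 8.3 instead requires at least one study treatment.
- SAP 7.2 defines TEAEs for controls as follows: "Not treated subjects: all documented AEs".
- SAP 7.2 plans the analyses by period and overall, "whereby only analysis for period 1 will be stratified by actual treatment arm". Period 1 tables therefore have a control column.

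The overall AE summary in SAP 7.2 limits its treatment-related rows, for example "Any treatment-related TEAEs (for treated subjects"). The incidence list that follows has no such limit on "TEAEs by worst causal relationship, subjects with TEAEs by PT", on the table of related events by worst intensity, or on the table of treatment-related events by SOC and PT. The related-event tables by Fitzpatrick group and gender at the end of SAP 7.2 have none either.

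**The concern.** Protocol 7.2.2 calls an AE related when a causal link to the investigational device is at least a reasonable possibility. In a subject who was never injected, that cannot hold. For treated subjects, imputing a blank as related is cautious. For a control, the same rule produces a value that is simply invalid.

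Two things are at stake. First, device- and injection-related events are a stated safety endpoint (SAP 6.2), and a programmer who follows the text literally could put such events in the control column. Second, the report could contradict itself: the overall summary would leave a control event out of its related rows while a detailed table counted it as related.

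**Working it through.** **Text check.** Take one Period 1 AE in a control with causality left blank, and apply the SAP as written.

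| Step | SAP section | Result |
|---|---|---|
| Is the subject in the safety population? | 5 | Yes |
| Is the event a TEAE? | 7.2 | Yes |
| Is causality imputed? | 7.4.1.2 | Yes, as *drug related* |
| Counted in the related rows of the overall summary? | 7.2 | No, limited to treated subjects |
| Counted as related in the three detailed tables? | 7.2 | Yes, no limit stated |
| Counted in the related-event subgroup tables? | 7.2 | Yes, no limit stated |

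If intensity were blank too, the event would appear as both severe and related.

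**Size.** The plan gives no figure to reproduce. The one documented input is the planned control arm of 22 (SAP 4.1). The number of controls with a blank causality item is not given.

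With k affected controls, the control related rate rises from 0 to k/22:
- k = 1: 1/22 = 4.5%
- k = 2: 2/22 = 9.1%
- k = 3: 3/22 = 13.6%

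To show how far the answer depends on unknowns, let q be the share of controls with an AE and m the share of those with causality missing. Both are assumptions. If controls are independent, the expected number affected is 22qm, and the chance of at least one is 1 − (1 − qm)^22.

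| q | m | Expected number, 22qm | Chance of at least one |
|---|---|---|---|
| 10% | 2% | 0.04 | 4% |
| 40% | 2% | 0.18 | 16% |
| 10% | 20% | 0.44 | 36% |
| 40% | 20% | 1.76 | 84% |

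Over this grid, fewer than two controls are expected to be affected. Only a systematic blank (m = 100%) gives larger numbers: 22 × 0.10 = 2.2 to 22 × 0.40 = 8.8 controls.

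In the subgroup tables the denominator is smaller, so one event weighs more. The documents do not fix the number of controls per subgroup, because randomization is stratified by site only. If the planned 30% share of skin types IV to VI carried over to controls (0.30 × 22 = 6.6, about 7), one event would be 1/7 = 14.3%.

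**After the fix.** With imputation limited to injected subjects, the imputed related count in the control column is 0/22 by construction.

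**The case against.** The strongest reply is that the rule will rarely act on controls. Protocol 7.2.4.1 lists causal relationship among the minimum items recorded for any AE, with no exception for controls. Protocol 7.2.2 says that without evidence or argument for a causal link, the event is to be considered not related. Data are also cleaned before the Month 2 lock. A reader might infer that causality is the item most likely to be blank for controls, since they receive nothing to which an event could be attributed. The documents do not support that: they point the other way, and the eCRF is not among them. Nor do they support any particular count of affected controls.

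It can also be said that the treated-subjects mark on the summary rows shows what the authors meant, and that the mark on the start-date rules follows from their content, since they place events relative to first injection. Both points are fair. The contrast within 7.4.1.2 does not show a deliberate extension to controls. But intent shown in one table does not bind the programming of others when the imputation rule says it covers every table.

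Finally, safety is descriptive and no between-arm safety test is planned, so no formal inference is affected. That stands, and it limits the severity.

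**Conclusion.** The gap in the text is real: a stated rule gives an invalid value whenever it meets a never-injected subject, and the result would conflict with the overall AE summary. It is minor. The effect is zero if every control AE has a recorded causality, which the protocol makes likely but cannot guarantee. Otherwise it is 4.5 percentage points in the control column per affected control, assuming 22 controls.

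A reader might go further and infer that the safety comparison is biased in favour of the device. The documents do not support that. Related-AE rates in treated subjects are untouched by anything imputed for controls, and the four related rows of the overall summary are already protected. The effectiveness results are not involved.

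**What to change.** In SAP 7.4.1.2, state that missing causality is imputed as *related* only for subjects who received at least one injection, and that it is not imputed for never-injected subjects but shown as not applicable. *Related* is the category in protocol 7.2.2 and should replace *drug related*, since the product is a device.

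In SAP 7.2, extend the treated-subjects limit from the overall summary to every table of related TEAEs or of causality, including the subgroup tables.

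The cost is one sentence, a few table titles and one programming condition, all before the Month 2 lock. No valid information is lost, because control AEs remain in the other TEAE tables and in the listings.

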7.4.2 Timing of statistical analyses

The time from the baseline visit to the end of study is thirteen months. The primary effectiveness endpoint is at Month 2 post last injection (i.e. either baseline treatment or touch-up, if applicable); however, treated subjects will continue to be followed for safety via in clinic visits at Months 3, 6, 9, and 12 after the last injection (i.e., either baseline treatment or touch-up, if applicable). For the purposes of the clinical study report (CSR), statistical analyses will be performed after all subjects have completed the Month 2 post last injection visit. At this time, the data will be cleaned and the database temporarily locked for all effectiveness and safety analyses corresponding to the Month 2 primary effectiveness endpoint. A CSR will be written for these data and an addendum will be made to the report based on additional safety analyses associated with the safety monitoring for treated subjects up to 12 months after the last injection (i.e., either baseline treatment or touch-up, if applicable).

7.4.3 Examination of Subgroups

The primary effectiveness (ITT using observed cases) and secondary effectiveness (ITT using observed cases) endpoints will be descriptively summarized after stratification into the following subgroups:

- Fitzpatrick Skin types (I-III versus IV-VI)
- Gender (males versus females)

The safety endpoints for incidences of TEAEs using the SP will be descriptively summarized after stratification in the aforementioned subgroups.

There will be no statistical comparisons made for all subgroup analyses.
